Appendix 1: Numerical Pain Scale NRS for Joint Pain	
Appendix 2 Disabilities of the Arm, Shoulder and Hand DASH	
Appendix 3 Patient Global Assessment	

1. LIST OF ABBREVIATIONS

ADE Adverse Device Effect

AE Adverse Event
CA Competent Authority

CFR Code of Federal Regulations

DMP Data Management Plan

DASH Disabilities of the Arm, Shoulder and Hand

EC Ethics Committee

FDA Food and Drug Administration

HA Hyaluronan / Sodium Hyaluronate / Hyaluronic Acid HIPAA Health Insurance Portability and Accountability Act

IA Intra-articular

ICF Informed Consent Form

ICH International Conference on Harmonization

IFU Instructions for Use

ISO International Organization for Standardization

ITT Intent to Treat

MedDRA Medical Dictionary for Regulatory Activities

OA Osteoarthritis

PGA Patient Global Assessment

Pl Principal Investigator

PP Per Protocol

SADE Serious Adverse Device Effect

SAE Serious Adverse Event SAP Statistical Analysis Plan

SOP Standard Operating Procedure

UADE Unanticipated Adverse Device Event

USADE Unanticipated Serious Adverse Device Effect

2. STUDY SYNOPSIS

T:41-	A December 10 March 1 Constant 1 March
Title	A Prospective Study of a Single Injection Cross-linked Sodium Hyaluronate (MONOVISC) to Provide Symptomatic Relief of Osteoarthritis of Shoulder Joint
Study	Obtain real world, post market data to confirm the clinical improvement and safety in
Objective	patients treated with a single injection of MONOVISC for the symptomatic relief of
	osteoarthritis in the shoulder joint.
Investigational	Monovisc®: A chemically cross-linked sodium hyaluronate supplied as a 4-mL unit dose
Product	in a 5-mL glass syringe.
Mode of	Monovisc will be injected into the intraarticular (IA) space of the index shoulder using an
Delivery	18-21 gauge needle.
Study Design	Prospective, multi-center, open label post market clinical follow up clinical trial.
Phase	Phase IV
Sample Size	25 subjects will be enrolled.
Study Duration	The entire study duration from first subject in to last subject out will be approximately one
	and half years. The enrollment phase will be approximately 12 months with a follow-up
	phase of 6 months. Visits will be scheduled at screening, baseline, 1 month, 3 months
	and 6 months post treatment. First patient in is expected August 2019.
Inclusion	Screening Inclusion Criteria
Criteria	1. Age 18 years or older
	2. Body Mass Index (BMI) ≤ 35 kg/m ²
	3. Diagnosis of symptomatic osteoarthritic joint in the index joint (Kellgren Lawrence
	grade I to III or Guyette grade I to III) to be treated with MONOVISC injection.
	4. Failed conservative treatment for joint osteoarthritis.
	 5. NRS pain ≥4 and ≤9 in the index joint. 6. Subject must be willing to abstain from other treatments of the index joint for the
	6. Subject must be willing to abstain from other treatments of the index joint for the duration of the study.
	7. Subject is willing to discontinue all analgesics including NSAIDs, except
	acetaminophen/paracetamol, at least seven days before the treatment injection and
	through the completion of the study.
	Subject is willing to use only acetaminophen/paracetamol (up to a maximum of 4.0
	grams per day per the package insert) for the treatment of joint pain for the duration
	of the study. At least forty-eight hours prior to the Baseline Visit and each follow-up
	visit, the subject is willing to discontinue use of acetaminophen/paracetamol.
	9. Subject is willing to maintain a stable dose of oral glucosamine and/or chondroitin
	sulfate products throughout the study, if taken prior to signing the informed consent
	form (ICF).
	10. Able and willing to provide signed informed consent.
	Screening Exclusion Criteria
	History of hypersensitivity to any of the ingredients in the hyaluronan
	2. Infection or skin disease in the area of the injection site or index joint
	3. NRS pain > 3 in the contralateral joint
	4. Subject received an injection of Hyaluronic Acid (HA) and/or steroid in either joint
	within 6 months of signing the informed consent form (ICF). A subject will be
	excluded if they are planning to receive an HA or steroid injection (other than the
	study injection) in either joint during the course of this study.
	5. Known inflammatory or autoimmune disorders (including rheumatoid arthritis, gout),
	or other pre-existing medical conditions that, in the opinion of the investigator, could
	impact treatment of the index joint or affect the ability of the subject to accurately
	complete the study questionnaires and comply with the study requirements. 6. Subject is taking medications at the time of signing the ICF which could interfere
	 Subject is taking medications at the time of signing the ICF which could interfere with the treatment procedure, healing and/or assessments. This includes but is
	not limited to oral or injectable anticoagulant treatments, anti-aggregant platelet
	treatment, chronic opioid analgesics. Low dose aspirin used for cardiovascular
	protection is allowed if a stable regimen is maintained for the duration of the
	study.
	otaay.

- 7. Subjects who had an oral, intramuscular, intravenous, rectal suppository or topical (excluded in index joint only) corticosteroid prior 30 days of signing the ICF are excluded. Topical corticosteroid use at any site other than the index joint is allowed.
- 8. Significant trauma to the index shoulder within 26 weeks of screening
- 9. Chronic use of narcotics or cannabis.
- 10. Ligament instability or tear in index joint.
- 11. Diagnosis of fibromyalgia
- 12. Diagnosis of osteonecrosis in index joint
- 13. Uncontrolled diabetes with HbA1c of >7%.
- 14. Subject is a woman who is pregnant or breastfeeding at the Screening Visit or a woman of child bearing potential who refuses to use effective contraception during the course of the study.
- 15. Subject is receiving or in litigation for worker's compensation.
- 16. Otherwise determined by the investigator to be medically unsuitable for participation in this study.

Baseline Inclusion Criteria

NRS pain ≥4 and ≤9

Baseline Exclusion Criteria

- Subject has a decrease of ≥ 2 in the NRS pain from Screening to Baseline in the index joint.
- 2. Subject has a contraindication to continue with the study treatment injection based on the visual appearance of the synovial fluid aspirate.

Criteria for Evaluation

Primary Endpoint:

 Reduction of index joint Numerical Rating Scale (NRS) pain from baseline to 6 Months post injection.

Secondary Endpoints:

- Improvement in DASH index from baseline to 6 months post injection.
- Improvement in Patient Global Assessment (PGA) from baseline to 6 months post injection.
- OMERACT-OARSI responder rate in the index joint at 6 months post injection.
- Time to treatment failure
- Reduction in Medication usage from baseline to 6 months post injection.

Exploratory Endpoints

Any comparisons across timepoints (baseline to 6 months) not described in the primary or secondary endpoints including but not limited to:

- Demographics
- Medical History
- History of joint osteoarthritis
- Rescue Medication Use
- Treatment Failure
- Injection procedure
- Concomitant medications

	Non-drug therapy
	Safety Endpoint:
	The incidence, severity, and relationship to treatment of all Adverse Events (AE) will be collected from the first treatment injection to the 6 month assessment.
Statistical Analysis	The primary analysis on the endpoints will be performed on the ITT (Intent to Treat) populations. All Primary and Secondary endpoints will be analyzed using the ITT population.
	A secondary analysis will be conducted on the Per Protocol (PP) population. Since the primary endpoint is at 6 months this is all subjects who complete the 6 month assessment and do not have a major deviation in the conduct of the protocol. For all other visits, this is defined as the subjects who complete those visits according to the protocol.
	All safety analyses will be conducted on all subjects who undergo treatment of MONOVISC in the shoulder joint.
Sites	Up to 20 clinical sites in EU
Sponsor	Anika Therapeutics, Inc. [name], United States of America
	Phone: + 1 [contact] Fax: + 1 [contact]

3. INTRODUCTION

MONOVISC® is Anika's next generation sodium hyaluronate device for treating joint pain. It has been designed to deliver comparable benefits to those of ORTHOVISC® with a single injection.

MONOVISC has previously shown clinical improvement when studied for osteoarthritis of knees. The MONOVISC 07-02 results show MONOVISC achieved a 44% improvement from baseline in WOMAC A scores.

Hyaluronic Acid injections in non-knee synovial joints has been reported to show benefits in pain reduction and improvement in joint function. Patients with hip osteoarthritis had significantly improved Lequesne's function and reduced VAS pain at 3 and 6 months after injection (Migliore et al. *Arthritis Research & Therapy* 2009 Vol 11 No 6). A study on the use of intra-articular HA in the treatment of symptomatic osteoarthritis of the shoulder showed an improvement in VAS score of 24 points from baseline to 6-months (Silverstein et al. *Am J of Sports Medicine*, 2007, Vol 35, No. 6). The effect of a single injection of HA on patients with symptomatic ankle (talo-crural) osteoarthritis show an improvement in VAS score of 44.5 points from baseline to 3 months (Witteveen A.G.H. et al. *I Foot and Ankle Surgery* 2008 *Vol* 14 p145-152).

The goal of this study is to demonstrate the clinical improvement and safety in patients treated with MONOVISC for shoulder osteoarthritis. Specifically, this study will provide confirmation to the effectiveness and safety of MONOVISC at relieving shoulder joint pain to 6 months post-treatment.

4. BENEFITS / RISKS

4.1 Benefits

Intra-articular injections of MONOVISC and other hyaluronic acid viscosupplements have shown significant clinical benefits for knee osteoarthritis patients. It is anticipated that such benefits may result from the use of MONOVISC to treat shoulder OA pain.

4.2 Risks

Any intra-articular injection poses potential risks. However, subjects should incur no additional risks compared to injections of other frequently injected products, such as corticosteroids or diagnostic contrast agents.

Adverse events associated with single intra-articular knee injections of MONOVISC can be found in the MONOVISC Instructions for Use. These events are expected to be similar for shoulder injections. In the clinical trial for MONOVISC in knee OA, adverse events that were related to the injection treatment were:

- injection site pain/swelling
- joint stiffness / swelling / effusion
- arthralgia,
- pain in extremity
- synovitis

- contusion
- subcutaneous nodule
- Baker's cyst

Adverse events not related to the index joint for MONOVISC were:

- arthralgia
- headache
- pain in extremity
- upper respiratory tract infection
- back pain

Other risks associated with intra-articular shoulder injections, regardless of treatment, include:

- · temporary injection site pain, swelling or tenderness
- temporary stiffness of the shoulder
- malfunction of the syringe and/or needle

In rare instances, side effects could include:

- an allergic reaction to the fluoroscopic imaging contrast agent. Symptoms could include redness or inflammation at the injection site or inside the shoulder joint, hives or itching.
- an allergic reaction to the local anesthetic (lidocaine). Symptoms could include redness or inflammation at the injection site or inside the shoulder joint, hives or itching.
- injection site infection
- neurovascular, cartilage, or bone damage resulting from the injection itself

Finally, there is a low risk associated with radiation from the X-ray evaluation required for inclusion in the study. There is also a low risk from the radiation during fluoroscopy-guided injections

5. Contraindications / Warnings and Precautions

5.1 Contraindications

The following contraindications are included in the package insert (AML 500-263/E):

Monovisc is composed of cross-linked sodium hyaluronate and may contain trace amounts of gram positive bacterial proteins. The following pre-existing conditions may constitute relative or absolute contraindications to the use of MONOVISC

- Known sensitivity to any of the materials contained in MONOVISC
- Pre-existing infections of the skin region of the intended injection site
- · Known infection of the index joint
- · Known systemic bleeding disorders

5.2 Warnings

There are no warnings specific to Monovisc (AML 500-263/E).

5.3 Precautions

The following precautions are cited in the package insert (AML 500-263/E):

- Those precautions normally considered during injection of substances into joints are recommended.
- Only medical professionals trained in accepted injection techniques for delivering agents to joint spaces should inject sodium hyaluronate for this application.
- The amount of Monovisc necessary to be injected depends on specific site and patient
 anatomy and needs to be defined by the medical professional performing the procedure. An
 excess quantity of sodium hyaluronate should not to be used and the patient should be
 monitored closely.
- The synovial space should not be overfilled.
- If pain increases during the injection procedure, the injection should be stopped and the needle withdrawn.
- Transient pain or swelling may occur after the intra-articular (IA) injection.
- As with any invasive joint procedure, it is recommended that patients avoid strenuous or prolonged (i.e., more than one hour) weight-bearing activities such as running or tennis within 48 hours following the intra-articular injection.
- Pregnancy: The safety and effectiveness of the use of MONOVISC® in pregnant women has not been tested.
- **Nursing Mothers:** It is not known if MONOVISC® is excreted in human milk. The safety and effectiveness of the use of the product in lactating women has not been tested.
- **Pediatrics**: The safety and effectiveness of the use of MONOVISC® in pediatric patients (≤ 21 years of age) has not been tested.

6. ENDPOINTS

6.1 Primary Endpoint:

Reduction of index joint Numerical Rating Scale (NRS) pain from baseline to 6 Months post injection.

6.2 Secondary Endpoints:

- Improvement in DASH index joint from baseline to 6 months post injection.
- Improvement in Patient Global Assessment (PGA) from baseline to 6 months post injection.
- OMERACT-OARSI responder rate in the index joint at 6 months post injection.
- Time to treatment failure
- Reduction in Medication usage from baseline to 6 months post injection.

6.3 Exploratory Endpoints

Any comparisons across timepoints (baseline to 6 months) not described in the primary or

Version 2.0 14 Aug 2019 Confidential Page 11 of 38

MON 18-02

secondary endpoints, including but not limited to:

- Demographics
- Medical History
- History of joint osteoarthritis
- Rescue Medication Use
- Treatment Failure
- Injection procedure
- Concomitant medications
- Non-drug therapy.

6.4 Safety Endpoint:

The incidence, severity, and relationship to treatment of all Adverse Events (AE) will be collected from the treatment injection to the 6 month assessment.

6.5 Trial Design

This is a prospective, post market clinical follow-up (PMCF) multi-center, open-label study to evaluate the residual risk of injections of MONOVISC for relief of pain in patients with a diagnosis of an osteoarthritic shoulder joint.

The subjects in this study will be patients with a diagnosis of osteoarthritic (OA) joint who the investigator determines are appropriate candidates for treatment with a viscoelastic injection of MONOVISC.

Up to 25 subjects will be enrolled at up to 20 investigational sites in the EU. Subject participation will last approximately 6 Months, with visits scheduled at Screening, Baseline, 1 month, 3 month and 6 months.

6.6 Enrollment Criteria

At screening visit:

- 6.6.1 Screening Inclusion Criteria
 - 1. Age 18 years or older
 - 2. Body Mass Index (BMI) $\leq 35 \text{ kg/m}^2$
 - 3. Diagnosis of symptomatic osteoarthritic joint in the index joint (Kellgren-Lawrence grade I to III or Guyette grade I to III) to be treated with MONOVISC injection.
 - 4. Failed conservative treatment for joint osteoarthritis.
 - 5. NRS pain ≥4 and ≤9 in the index joint.
 - 6. Subject must be willing to abstain from other treatments of the index joint for the duration of the study.
 - 7. Subject is willing to discontinue all analgesics including NSAIDs, except acetaminophen/paracetamol, at least seven days before the treatment injection and through the completion of the study.
 - 8. Subject is willing to use only acetaminophen/paracetamol (up to a maximum of 4.0 grams per day per the package insert) for the treatment of joint pain for the duration of the study. At least forty-eight hours prior to the Baseline Visit and each follow-up assessment, the subject is willing to discontinue use of acetaminophen/paracetamol.
 - 9. Subject is willing to maintain a stable dose of oral glucosamine and/or chondroitin sulfate products throughout the study, if taken prior to signing the informed consent form (ICF).
 - 10. Able and willing to provide signed informed consent.

6.6.2 Screening Exclusion Criteria

- 1. History of hypersensitivity to any of the ingredients in the hyaluronan
- 2. Infection or skin disease in the area of the injection site or index joint
- 3. NRS pain \geq 3 in the contralateral joint
- 4. Subject received an injection of Hyaluronic Acid (HA) and/or steroid in either joint within 6 months of signing the informed consent form (ICF). A subject will be excluded if they are planning to receive an HA or steroid injection (other than the study injection) in either joint during the course of this study.
- 5. Known inflammatory or autoimmune disorders (including rheumatoid arthritis, gout), or other pre-existing medical conditions that, in the opinion of the investigator, could impact treatment of the index joint or affect the ability of the subject to accurately complete the study questionnaires and comply with the study requirements.

6. Subject is taking medications at the time of signing the ICF which could interfere with the treatment procedure, healing and/or assessments. This includes but is not limited to oral or injectable anticoagulant treatments, anti-aggregant platelet treatment, chronic opioid analgesics. Low dose aspirin used for cardiovascular protection is allowed if a stable regimen is maintained for the duration of the study.

- 7. Subjects who had an oral, intramuscular, intravenous, rectal suppository or topical (excluded in index joint only) corticosteroid within 30 days of signing the ICF are excluded. Topical corticosteroid use at any site other than the index joint is allowed.
- 8. Significant trauma to the index shoulder within 26 weeks of screening.
- 9. Chronic use of narcotics or cannabis.
- 10. Ligament instability or tear in index joint.
- 11. Diagnosis of fibromyalgia
- 12. Diagnosis of osteonecrosis in index joint
- 13. Uncontrolled diabetes with a HbA1c of >7%.
- 14. Subject is a woman who is pregnant or breastfeeding at the Screening Visit or a woman of child bearing potential who refuses to use effective contraception during the course of the study.
- 15. Subject is receiving or in litigation for worker's compensation.
- 16. Otherwise determined by the investigator to be medically unsuitable for participation in this study.

At baseline visit:

- 6.6.3 Baseline Inclusion Criteria
 - 1. NRS pain ≥4 and ≤ 9
- 6.6.4 Baseline Exclusion Criteria
 - Subject has a decrease of ≥ 2 in the NRS pain from Screening to Baseline in the index joint.
 - 2. Subject has a contraindication to continue with the study treatment injection based on the visual appearance of the synovial fluid aspirate.

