7.4 Baseline Visit: Treatment Visit (Day 0)

The Baseline Visit (Day 0) will occur 7 to 14 days after the Screening Visit to allow for rescue medication washout. The injection will occur at this Baseline visit along with the following activities:

Before Treatment Injection

- Concomitant Medications
- Current non-drug therapies
- Confirm Medication Washout
 - If subject did not complete medications washout, reschedule the visit to allow washout to be completed.
- Patient Global Assessment (PGA)
- DASH index shoulder
- Index & Contralateral Shoulder Joint Pain (NRS Scale)
 - o Confirm Baseline Inclusion & Exclusion Criteria for NRS pain
- Physical Exam of Index and Contralateral Shoulder Joints

Treatment Procedure

The Treating Physician will always perform the Study Injection to the index joint as standard of care dictates.

Intra-articular injection of the shoulder joint should be conducted under fluoroscopic or ultrasound guidance. Guidelines for the injection procedural steps are provided below. Modifications to this technique should be recorded in the CRF

- Patient may be sitting or supine as required.
- Prep the skin at injection site with 1% betadine solution or equivalent.
- Peri- articular injection site anesthesia of lidocaine or topical refrigerant anesthetic (e.g. ethyl

chloride) may be utilized.

- Use fluoroscopic or ultrasound guidance to insert 18-22 1 cm lateral and 1 cm cephalad to the coracoid process. Insert the needle directed 20° medially and 60° caudally to enter the joint.
- Insert needle until resistance against the articular surface and then withdraw the needle 1-2 mm.
- If using fluoroscopic guidance, a small amount of fluoroscopic contrast agent (0.5 to 1.0 ml) should be injected through the needle to verify intra-articular placement.
- If using ultrasound guidance, a small volume of air (up to 0.5 ml) may be injected to verify IA positioning.
- If pooling of the contrast agent or air around the needle tip is observed, the needle should be repositioned.
- When contrast agent or air is successfully injected into the joint, intra-articular placement is confirmed.
- Following confirmation of intra-articular needle placement, the joint may be aspirated to remove synovial fluid.
 - o Confirm the Baseline Exclusion for synovial aspirate.
- 4 ml of MONOVISC is injected into the joint.
- Intra-articular anesthetic should NOT be administered as part of the injection procedure.

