9. STATISTICAL CONSIDERATIONS

9.1 Sample Size

The primary analysis will be the mean change in index joint pain from baseline to 6 months as measured by the Numerical Rating Scale.

The hypothesis to be tested is:

 H_0 : $\mu_{DMON} = 0$ versus H_A : $\mu_{DMON} > 0$.

In this hypothesis, μ_{DMON} is the mean change in pain from baseline at 6 Months in MONOVISC treated patients.

The data will be analyzed via a one sample t-test.

It is assumed that a mean change in pain from baseline of 2 points represents a clinically significant improvement with a standard deviation of 2 - 2.5 points, for 80% power and alpha of 5% then a total of 15 subjects are required. To ensure sufficient subjects are available at the 6 month follow up, it is proposed to enroll and treat at least 25 subjects which should be more than adequate to demonstrate that treatment of the study population with MONOVISC would reduce joint pain at 6 months.

Sites should not enroll more than 50% of the total enrollment.

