9.2 Statistical Methods

Anika Therapeutics, Inc.

Tabulation of summary statistics, graphical presentations, and statistical analyses will be performed. Where not otherwise specified, the last pre-treatment observation will be used as baseline for calculating post-treatment changes from baseline. The primary presentations and analyses will be based on data pooled across index lesion locations and across study centers. Relevant summaries for individual lesion locations and centers, or combinations of index lesions and centers, may be presented for primary data. All testing and confidence intervals will use a significance level of 5%.

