#### 4.1.2 Primary Efficacy Endpoint

# 4.1.2.1 The mean change in index joint Pain from baseline to 6 Months as measured with NRS comparing the Monovisc treated group to baseline measurements.

The primary analysis will be the mean change in index joint pain from baseline to 6 months as measured by the Numerical Rating Scale.

The hypothesis to be tested is:

```
H_0: \mu_{DMON} = 0 versus H_A: \mu_{DMON} > 0.
```

In this hypothesis,  $\mu_{DMON}$  is the mean change in pain from baseline at 6 Months in MONOVISC treated patients.

The data will be analyzed via a one sample t-test.

This will be analyzed using SAS PROC UNIVARIATE. ODS statements will be used to output the descriptive statistics and p-values into data sets that can be easily displayed using PROC REPORT.

The tables for this analysis will be displayed as follows showing all time points for reference:

This analysis will be performed for each of the protocols

Summary of Differences in Mean Responses over time -

| Time Perios |                       |                 | Visit Result |                      |
|-------------|-----------------------|-----------------|--------------|----------------------|
|             | Descriptive Statistic | Baseline Result |              | Change from Baseline |
| 1 Week      | N                     |                 |              |                      |
|             | Mean                  |                 |              |                      |
|             | Std.Drv               |                 |              |                      |
|             | Median                |                 |              |                      |
|             | (Min,Max)             |                 |              |                      |
|             | p-value diff=0        |                 |              |                      |
| 1 Month     | N                     |                 |              |                      |
|             | Mean                  |                 |              |                      |
|             | Std.Drv               |                 |              |                      |
|             | Median                |                 |              |                      |
|             | (Min,Max)             |                 |              |                      |
|             | p-value diff=0        |                 |              |                      |

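### The Day 0 pain score decides entry, by a rule that limits falls more than rises, and is then the baseline of an uncontrolled test against zero, so a zero mean change is not the no-effect value

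*Protocol*

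**What the plan says.** Protocol 6.6.1 requires "NRS pain ≥4 and ≤9 in the index joint" at Screening. Section 6.6.3 applies the same window, "NRS pain ≥4 and ≤ 9", at Baseline. Section 6.6.4 then excludes a subject if "Subject has a decrease of ≥ 2 in the NRS pain from Screening to Baseline in the index joint". No criterion limits a rise between the two visits, except that the Baseline score may not exceed 9.

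The eligibility check uses the score taken before injection on Day 0. The pre-injection list in Protocol 7.4 includes "Confirm Baseline Inclusion & Exclusion Criteria for NRS pain". That score is also the comparator. Under Protocol 9.2, "the last pre-treatment observation will be used as baseline for calculating post-treatment changes from baseline", and SAP 4.2 has the same rule.

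On the analysis, Protocol 9.1 says "The primary analysis will be the mean change in index joint pain from baseline to 6 months as measured by the Numerical Rating Scale". Protocol 9.1 and SAP 4.1.2.1 specify a one-sample t-test with a null mean change of zero and a one-sided alternative. The study is open label with no comparator (Protocol 6.5). Section 9.1 (repeated in SAP 4.1.1) calls 25 subjects "more than adequate to demonstrate that treatment of the study population with MONOVISC would reduce joint pain at 6 months". Neither document mentions regression to the mean, a second baseline reading or a non-zero benchmark.

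**The concern.** A single NRS reading is the subject's underlying pain plus visit-to-visit error. Subjects whose Day 0 reading was low by chance tend to be removed, by the 4-point floor or because the reading fell 2 or more from Screening. Subjects whose reading was high by chance mostly stay. In those enrolled, the average Day 0 error can therefore be above zero. At Month 6 the error is drawn afresh, and the mean falls back with no treatment effect.

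Two things are at stake. The primary estimate may be biased towards benefit. And the nominal 5% error rate applies to the statement that mean change is zero, whereas Section 9.1 draws a conclusion about what treatment does.

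**Working it through.** **1. The plan's own figure.** Inputs from Protocol 9.1: change 2 points, SD 2 to 2.5, power 80%, alpha 5%. For a one-sample t-test, power comes from the noncentral t with noncentrality (2/SD)·√n.
- Two-sided, SD 2.5: n = 15, power 82.1%. This reproduces the stated 15.
- One-sided, SD 2.5: n = 12. Two-sided, SD 2: n = 10. One-sided, SD 2: n = 8.

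The stated 15 matches a two-sided test while the alternative is written one-sided, so both are shown below.

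**2. Model for an inert injection.** Score = true pain + visit error, rounded and clipped to 0–10. Screening, Baseline and Month 6 share the same true pain and have independent errors. The entry rules are applied as written, and change = Baseline − Month 6.

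Assumptions that are not in the documents: true mean 5.5 to 6.5, between-subject SD 1.2 to 1.5, visit-error SD 1.6 to 2.0. These give an SD of change of 2.0 to 2.4, close to the plan's 2 to 2.5.

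**3. Results at n = 25, no treatment effect.**

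| Scenario | Apparent reduction | One-sided 5% test rejects | Two-sided 5% test rejects |
|---|---|---|---|
| Stable pain, entry rules as written | about 0.4 to 0.75 | about 22–45% | about 14–33% |
| Smaller visit noise (SD of change below 1.5) | smaller | about 12–22% | – |
| Washout rise of 0.5 point at Baseline and Month 6 | smaller | about 7–26% | – |
| Washout rise of 1 point at Baseline and Month 6 | near zero in places | about 2–14% | – |

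The low ends of the washout rows come from a true mean near 7, where the cap of 9 removes high readings. At mean 7, between-subject SD 1.5 and SD of change 2, one-sided rejection is 6.8% for a 0.5-point rise and 2.4% for a 1-point rise.

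A wider grid with stable pain and independent errors (mean 5 to 7, between-subject SD 1 to 2) gives a reduction of 0.23 to 0.81 and one-sided rejection of about 15–55%. If the Screening and Baseline errors correlate at 0.5, it is about 7–47%.

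**4. Hand check of the first row.** Rejection is roughly P(Z > t-critical − bias·√25/SD). The one-sided critical value on 24 df is 1.711.
- Bias 0.37, SD 2.0: 0.37 × 5/2.0 = 0.925; 1.711 − 0.925 = 0.786; P = 22%.
- Bias 0.75, SD 2.4: 0.75 × 5/2.4 = 1.56; 1.711 − 1.56 = 0.15; P = 44%.

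Against the 2-point change, these biases are 0.37/2 = 18% and 0.75/2 = 38%.

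**5. Which rule is responsible.** With the fall-of-2 rule removed and the 4–9 windows kept, the bias in the step 2 settings is 0.02 to 0.39. The rule itself adds about 0.31 to 0.42, and the 4-point floor accounts for the rest. If the same selected subjects are compared with a separate pre-injection score not used for entry, the bias is 0.00 and rejection is 4.7–5.3%. The cause is therefore the reuse of the entry score as comparator.

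**6. Alternative comparators from data already collected, without washout.**
- Mean of Screening and Baseline: bias 0.02 to 0.36, one-sided rejection about 5–19%.
- Screening alone: bias about −0.05 to −0.47. It is negative because the same rule favours low Screening readings.

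A washout rise lowers the first by about half the rise and the second by about the whole rise, apart from selection. With a 1-point rise the Screening-only bias is about −0.8 to −1.2.

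**The case against.** The strongest reply is that the size is conditional. Mean pain, between-subject spread and visit noise appear in neither document. The model assigns the whole planned SD of change to measurement noise, although real six-month change and variable response must be part of it. Less noise means less bias.

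The plan also contains a force in the other direction. Analgesics other than paracetamol stop at least seven days before injection (6.6.1), paracetamol stops 48 hours before Baseline and each follow-up (7.3.9.2), and Baseline is timed to allow washout (7.4). Pain may rise from Screening to Baseline, and fewer subjects would then meet the exclusion. All of this stands, and it is why a range is given that reaches 5% and below.

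A second reply is that no baseline definition lets a single-arm, open-label study separate product effect from placebo response or natural course. That is true, and it is a reason to soften the wording of 9.1. It does not excuse an avoidable further bias in the estimate.

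A third is that the alternative comparators are themselves biased. That also stands. An inert injection can still reject well above 5% with the averaged comparator, and the Screening-only comparator works against the product. Neither can serve as a criterion for calling the result robust.

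**Conclusion.** The point holds in a limited form. The mechanism follows from the documents: entry is selected on the Day 0 score, that score is the baseline, the test is uncontrolled and against zero, and nothing corrects for it. A mean change of zero is therefore not the value expected with no effect of MONOVISC.

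The size rests on assumptions. It is about 0.4 to 0.75 points and 22 to 45% one-sided rejection with stable pain and the plan's own order of SD. It is about 12 to 22% with smaller noise, and about 2 to 26% with a washout rise of 0.5 to 1 point.

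Three stronger readings are tempting, and the documents do not support them:
- That an inert injection would certainly be declared effective far more often than 5% of the time. The planned washout alone could remove the inflation.
- That the fall-of-2 rule is the sole cause, or that rises are unlimited. The 4-point floor contributes, falls of 1 point are kept if the score stays at 4 or above, and rises ending above 9 are excluded.
- That selection could produce the 2-point change. The bias is well below it. The weakness lies in testing against zero.

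**What to change.** Keep the primary t-test and the entry criteria. In SAP 4.1.2.1, pre-specify two sensitivity analyses of the primary endpoint:
- (a) baseline taken as the mean of the Screening and Baseline NRS;
- (b) baseline taken as the Screening NRS alone.

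Show both beside the primary result, each with its 95% confidence interval. State in the SAP that they form an approximate bracket, not a pass/fail test. Analysis (a) may keep some upward bias, and (b) is biased against the product by the same entry rule and by Screening scores taken on analgesics.

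In Protocol 9.1, SAP 4.1.1 and the report, replace the claim that the sample is "more than adequate to demonstrate that treatment of the study population with MONOVISC would reduce joint pain at 6 months" with an aim of estimating the mean within-patient reduction from baseline after injection. Add that this reduction includes regression to the mean and cannot be attributed to MONOVISC by this test alone.

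The cost is a few lines of text and one extra table. No new data are needed, because the Screening NRS is already in the Schedule of Events. The downside is that the Screening-based estimates mix on- and off-analgesic scores. A separate pre-injection score not used for entry would be cleaner, but it needs data the plan does not collect.
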